22.3.5 Adverse Event Start and Stop Dates

Imputation of partially or completely missing dates will be included in the data to document the treatment-emergent status of the adverse event and assignment of the adverse event to a reporting period. For an adverse event with an imputed start date, the classification of the event as treatment-emergent will depend only on whether the imputed date is the same as the date of infusion and not the timepoint of the infusion, since start times for adverse events will not be imputed. No duration will be calculated for adverse events with incomplete start-or-stop dates or for ongoing adverse events.

Imputation will follow the algorithm below. If an imputed start date after this procedure is after the end date, the start date will be set to the end date.

Start Dates

Participants With No IMP Infusion

For participants who have not been treated, the imputation of the adverse event start date will be performed as follows, where UK and UKN indicate unknown or missing day and month, respectively:

- UK-MMM-YYYY: The start date will be imputed with either the first day of the month or the date of Visit 1. The date of Visit 1 will be used if that is the later of the two and if it is within the specified month and year
- UK-UKN-YYYY: The start date will be imputed with either JAN 1 or the date of Visit 1. The date of Visit 1 will be used if it is within the specified year.

If the adverse event start date is completely missing, it will be set equal to the date of Visit 1.

Participants Who Received an IMP Infusion

For participants who have been treated, the imputation of adverse event start dates will be performed as follows:

UK-MMM-YYYY:

- If the year and month are equal to the year and month of treatment start date, the adverse event start date is imputed with the date of the dosing of IMP

- If the year is equal to the year of treatment start date: If the month is prior to the treatment start date, the adverse event start date is imputed with the last day of the month. If the month is equal to the month of the treatment start date, see above. If the month is after the month of the treatment start date, the adverse event start date is imputed with the first day of the month
- If the year is prior to treatment start date, the adverse event start date is imputed with the last day of the month
- If the year is after the year of treatment start date, the adverse event start date is imputed with the first day of the month

UK-UKN-YYYY:

- If the year is equal to the year of treatment start date, the adverse event start date is imputed with treatment start date
- If the year is prior to the year of treatment start date, the adverse event start date is imputed with 31-DEC-YYYY
- If the year is after the year of treatment start date, the adverse event start date is imputed with 01-JAN-YYYY

If the adverse event start date is completely missing, it will be set equal to treatment start date.

End Dates

Missing adverse event end dates will not be imputed.

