16.9 Safety Analyses

16.9.1 Analysis of Adverse Events

Adverse events will be classified according to the time of onset of the adverse event:

- *pre-treatment adverse event* – an adverse event that starts on or after the date the patient signed the *Informed Consent Form* and prior to the date of first dose of IMP
- *treatment-emergent adverse event* – an adverse event that starts or increases in intensity on or after the date of first dose of IMP

Adverse events, sorted by system organ class and preferred term, will be summarized by treatment group.

Allocation of TEAEs to Study Periods

TEAEs may be allocated to study periods (these will be defined in the SAP).

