13.1.3 Classification of Adverse Events

Adverse events will be classified according to the time of onset of the adverse event:

- *pre-treatment adverse event* – an adverse event that starts on or after the date the participant signed the *Informed Consent Form* and prior to the date and time of the dose of IMP.
- *treatment-emergent adverse event (TEAE)* – an adverse event that starts during or after administration of the dose of IMP, or a pre-treatment adverse event that increases in intensity or becomes serious during or after administration of the dose of IMP.

For handling of adverse events with incomplete start dates to facilitate this classification, see section 22.3.5. Note that adverse events with incomplete start dates will be classified as treatment-emergent simply if the imputed start date is on or after the date of IMP infusion, since the start time of the adverse event will not be imputed, unless the investigator in such a case has assessed that the causality to IMP is *not related - prior to IMP*.

An adverse event is considered causally related to the use of the IMP when the causality assessment by the investigator is *probable* or *possible*. If the causality assessment is missing, the adverse event is considered possibly causally related.

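### SAP 22.3.5 and 13.1.3 give different tests for treatment-emergent status when an adverse event start date is imputed; 22.3.5 is wrong as written and should be aligned with 13.1.3 (low priority)

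*SAP*

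**What the plan says.** Two sections of the SAP address treatment-emergent status when the start date is incomplete.

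- SAP 22.3.5 (Adverse Event Start and Stop Dates) has this rule for events whose start had to be filled in: "the classification of the event as treatment-emergent will depend only on whether the imputed date is the same as the date of infusion". The sentence continues "and not the timepoint of the infusion, since start times for adverse events will not be imputed".
- SAP 13.1.3 (Classification of Adverse Events) refers to 22.3.5 for handling incomplete start dates. It then says that these events "will be classified as treatment-emergent simply if the imputed start date is on or after the date of IMP infusion". It makes an exception where the investigator has given the causality as *not related - prior to IMP*.

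The general definitions agree with 13.1.3. SAP 13.1.3 defines a treatment-emergent event as "an adverse event that starts during or after administration of the dose of IMP", or a pre-treatment event that worsens. Protocol 16.9.1 has "an adverse event that starts or increases in intensity on or after the date of first dose of IMP".

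For treated participants, 22.3.5 also sets the imputation. A day-unknown event in the infusion month goes to the infusion date. The rule for later months reads "If the month is after the month of the treatment start date, the adverse event start date is imputed with the first day". Earlier months go to their last day. Year-only dates go to the infusion date in the infusion year, to 1 January in a later year and to 31 December in an earlier year. A completely missing start date goes to the infusion date.

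**The concern.** Equality with the infusion date is narrower than on or after it, and the imputation rules make the difference matter. The first of a later month, or 1 January of a later year, can never equal the infusion date. Such an event clearly began after dosing, yet it fails the 22.3.5 test. It would not fit the pre-treatment class either, because that class requires onset before the dose.

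The word *only* also leaves no room for the investigator exception in 13.1.3. That exception matters most for infusion-month events, which are all moved to the dosing date whether they began before or after it.

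The TEAE summaries in SAP 13.1.5 are the main adverse-event output. Their derivation should not depend on which of two sections a programmer reads.

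**Working it through.** The plan states no figure on this point, so there is none to reproduce. The check applies the imputation to each partial-date pattern and then measures how often the two tests differ.

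**Inputs.** The imputation rules and the equality test come from SAP 22.3.5. The on-or-after test comes from SAP 13.1.3. Follow-up to Week 12 (84 days) comes from SAP 4.2.

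**Step 1: classify each pattern.** Example infusion date: 15 Nov 2022.

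| Recorded start | Imputed start | 22.3.5 read literally | 13.1.3 |
|---|---|---|---|
| Oct 2022, day unknown | 31 Oct 2022 | not TEAE | not TEAE |
| Nov 2022, day unknown | 15 Nov 2022 | TEAE | TEAE |
| Dec 2022, day unknown | 1 Dec 2022 | **not TEAE** | **TEAE** |
| Jan 2023, day unknown | 1 Jan 2023 | **not TEAE** | **TEAE** |
| Feb 2023, day unknown | 1 Feb 2023 | **not TEAE** | **TEAE** |
| 2021 only | 31 Dec 2021 | not TEAE | not TEAE |
| 2022 only | 15 Nov 2022 | TEAE | TEAE |
| 2023 only | 1 Jan 2023 | **not TEAE** | **TEAE** |
| Completely missing | 15 Nov 2022 | TEAE | TEAE |

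The tests differ in exactly two situations: day unknown in a month after the infusion month, and year only in a year after the infusion year.

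**Step 2: share of day-unknown post-dose events affected on the literal reading.** Take onset as uniform over days 0 to 84, which is 85 days. Let r be the number of days left in the infusion month, counting the infusion day. The share falling in later months is (85 − r) / 85.

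- Infusion on 15 November: r = 16, so 69/85 = 81.2%.
- Infusion on the first of a 31-day month: r = 31, so 54/85 = 63.5% (the minimum).
- Infusion on the last day of a month: r = 1, so 84/85 = 98.8% (the maximum).
- Average over all infusion dates in a 365-day year: a month of n days contributes n(n+1)/2 to the sum of r. Mean r = (7 × 496 + 4 × 465 + 406) / 365 = 5738/365 = 15.72, so (85 − 15.72)/85 = 81.5%.

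For the 4-week treatment period (days 0 to 28, 29 days) the same count averages 46.0%, with a range of 0% to 96.6%.

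**Step 3: the same events under the on-or-after test.** Every event with true onset on days 0 to 84 is imputed either to the infusion date or to the first of a later month. Both are on or after infusion, so the loss is 0%. The 22.3.5 rule that moves an imputed start back to the end date does not alter this. The imputed start of a true post-dose event is never later than its true onset, and so never later than its end date.

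**The case against.** The strongest reply is that the sentence in 22.3.5 has to be read to its end. Its second half contrasts the date of infusion with the time of infusion, so *only* most naturally means date rather than clock time. SAP 13.1.3 is the section headed as the classification of adverse events. It uses 22.3.5 as a source of imputed dates and then states the correct rule for this case. The imputation also has separate branches for before and after dosing, which would serve little purpose if events on both sides of the infusion date were non-treatment-emergent.

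This reply stands as an account of intent, and it limits the point. A reader might infer that later-month events will drop out of the TEAE tables. The documents do not support that as a fact, because it requires a programmer to apply one sentence of 22.3.5 literally and set 13.1.3 aside. Nothing visible gives 22.3.5 precedence. Nor would all partially dated post-dose events be lost on the literal reading, since those imputed to the infusion date stay treatment-emergent.

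A reader might also infer that known pre-infusion events will be counted as treatment-emergent. The 13.1.3 exception covers events the investigator has placed before dosing, and the end-date rule in 22.3.5 moves events that ended before the infusion date back before it.

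The reply does not remove the discrepancy. The words in 22.3.5 still state an equality, no visible text says which section prevails, and the exception is missing from 22.3.5.

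**Conclusion.** The two sections state different tests, and the one in 22.3.5 is wrong as written. The size is conditional. If the sentence were programmed literally in place of 13.1.3, about 82% of day-unknown post-dose events over days 0 to 84 would be missed, plus year-only events in a later year. The 82% assumes uniform onset and an average over infusion dates; the share would be lower if events cluster soon after dosing, as the 4-week figure shows. The documents give neither a count of partially dated events nor a basis for estimating one, so no number of lost events should be inferred.

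Fully dated events are unaffected, and no safety summary changes if 13.1.3 is followed. A misclassified event would also remain visible, because SAP 13.1.4 lists all adverse events with a TEAE flag. This is a low-priority correction to a safety derivation rule.

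**What to change.** In the 22.3.5 sentence on imputed start dates, replace the condition that the imputed date is the same as the infusion date with the condition that it is on or after the infusion date. Keep the clause saying that dates rather than times are compared. Add a cross-reference to 13.1.3, including its *not related - prior to IMP* exception, so that both sections state one rule.

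The cost is one sentence in the SAP, with no new data collection and no extra analysis.

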10.1.3 Study-specific Adverse Event Definitions

10.1.3.1 Infusion-related Reactions

An *IRR* is any sign or symptom experienced by a patient during the infusion of the IMP or any event occurring on the day of the IMP infusion after the infusion was started.

Clinical manifestations of IRRs vary. Examples of IRRs include anaphylactoid reactions, anaphylaxis, dizziness, flushing, hypotension, nasal congestion, nausea, and syncope.

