13.1.5 Presentation of Treatment-emergent Adverse Events

The following summaries will be provided for the APTS:

- TEAEs by SOC and preferred term
- TEAEs by preferred term
- TEAEs by sex and preferred term
- TEAEs with an incidence $\geq 2\%$ and 5% in any treatment group by preferred term
- causally related TEAEs by SOC and preferred term
- TEAEs by severity (*mild/moderate/severe*), SOC, and preferred term
- causally related TEAEs by severity, SOC, and preferred term
- TEAEs occurring on the day of dosing after infusion start by SOC and preferred term

For TEAEs occurring on the day of dosing after infusion start, TEAEs with missing start times will also be included.

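### Adverse events dated to the infusion day only by imputation can be counted in the day-of-dosing table, because SAP 13.1.5 does not separate recorded from imputed start dates (minor)

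*SAP*

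**What the plan says.** SAP 22.3.5 gives the start-date rules for participants who received an infusion. Three of them lead to the infusion date:

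- Month and year known, both equal to those of the infusion: "the adverse event start date is imputed with the date of the dosing of IMP".
- Year only: "If the year is equal to the year of treatment start date, the adverse event start date is imputed with treatment start date".
- Nothing known: "If the adverse event start date is completely missing, it will be set equal to treatment start date".

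Other partial dates go elsewhere. A month before or after the infusion month goes to its last or first day respectively. For a year alone, the SAP says "If the year is prior to the year of treatment start date, the adverse event start date is imputed with 31-DEC-YYYY" and "If the year is after the year of treatment start date, the adverse event start date is imputed with 01-JAN-YYYY". If the imputed start falls after a recorded end date, the end date is used instead. Start times are not imputed. The section gives two purposes for the imputation: documenting treatment-emergent status and assigning a reporting period.

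SAP 13.1.3 classes an incompletely dated event as treatment-emergent if its imputed date is on or after the infusion date, unless the investigator's causality entry places it before IMP.

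SAP 13.1.5 plans a table of TEAEs that begin on the dosing day once the infusion has started, and adds for that table: "TEAEs with missing start times will also be included". It does not mention imputed dates.

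Protocol 10.1.3.1 counts as an infusion-related reaction any sign or symptom during the infusion, or "any event occurring on the day of the IMP infusion after the infusion was started".

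**The concern.** An imputation rule can suit one use and not another. Placing an undated event on the infusion date errs on the safe side when the question is whether it is treatment-emergent. When the question is whether it began on that particular day, the same rule supplies an answer that nobody recorded. Such an event has no start time, and 13.1.5 lets events without a start time through.

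What is at stake is how this one safety table reads. Its scope coincides with the protocol's definition of an infusion-related reaction to an intravenous antibody, so readers are likely to use it for that purpose. A count that mixes observed dosing-day events with events of unknown day is harder to interpret, and the table alone does not show which are which. The primary endpoint and the overall TEAE tables are not affected.

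**Working it through.** The plan gives no figure on this point, so there is none to reproduce. The check traces the rules and then sizes their effect under stated assumptions.

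**1. Route into the table**

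- Date (22.3.5): infusion date in the three cases above.
- Time (22.3.5): not imputed, so missing unless a time was entered without a date.
- Status (13.1.3): imputed date equals the infusion date, so the event is a TEAE unless the causality exception applies.
- Table (13.1.5): dosing day, time missing, therefore admitted. No stated condition removes it.

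Example, infusion on 10 March:

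- True onset 28 March, recorded as March: placed on 10 March, 18 days early, and can enter the table.
- True onset 20 April, recorded as April: placed on 1 April, does not enter.
- True onset 30 May, recorded as the year only or left blank: placed on 10 March, 81 days early, and can enter.

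**2. Share placed on the infusion date**

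Assumptions, not in the documents: infusion dates uniform over one calendar year; onset uniform over Days 0 to 84 (the 12-week follow-up of SAP 4.2); no earlier end date. The true Day 0 share is then 1/85 = 1.2%. Every true Day 0 event is placed on Day 0 under each rule, so the share of placements that are right is (1/85) divided by the share placed.

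| What is recorded | Share placed on Day 0 | Share of placements that are right |
|---|---|---|
| Nothing | 100% | 1.2/100 = 1.2% |
| Year only | 88.5% | 1.18/88.5 = 1.3% |
| Month and year | 18.5% | 1.18/18.5 = 6.4% |

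Cross-check for month and year: in a 30-day month with the dosing day uniform and onset constant from dosing onward, there are 30 dosing days among 1 + 2 + ... + 30 = 465 days at risk, and 30/465 = 6.5%. If onset is uniform over the whole month, pre-dose days included, the figure is 1/30 = 3.3%.

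**3. Onsets during screening (Days -28 to -1)**

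With no recorded end date, 100% (nothing recorded), 96.0% (year only) and 52.3% (month and year) are placed on the infusion date. With an end date recorded one day after onset, the end-date rule cuts each to about 3.5%: in essence only onsets on Day -1 remain, 1/28 = 3.6%. The causality exception can remove more.

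**4. Weight of one misplaced participant**

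Planned arms are 92, 46 and 92 (Protocol 3.1). One participant is 1/92 = 1.1 percentage points or 1/46 = 2.2. For an assumed one to three misplacements in a row of the table, the addition is 1.1 to 3.3 points (3/92) or 2.2 to 6.5 points (3/46). A participant already counted in that row adds nothing, since SAP 13.1.1 counts each participant once per preferred term.

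**5. What cannot be computed**

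Neither document says how many events are expected to have incomplete dates, so steps 2 to 4 give proportions and unit weights, not an expected count.

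**The case against.** The strongest defence is that 22.3.5 gives the imputation two purposes, and this table is neither. On that reading a programmer would not use imputed dates here. The sentence in 13.1.5 also has an ordinary reason: Protocol 10.3 collects a start time only for events shorter than 24 hours, so longer dosing-day events have a recorded date and no time and would otherwise be lost. Both points stand, and they make entry into the table an inference rather than something the SAP states. They do not close the gap. The section does not say that imputed dates serve only those purposes, and it keeps them in the data. It does bar one other use, since no duration is calculated for incompletely dated events, but it sets no such bar for this table. Two programmers could produce different counts.

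Other limits also stand. The end-date rule and the causality exception remove some events, mainly those from before the infusion. SAP 13.1.1 lists dates as collected, so a reader who goes to the listings can find the imputed events. Reactions are also checked on site during the infusion and for at least 2 hours afterwards (Protocol 8.3).

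A reader might infer that every event known only to the month or year lands on the infusion date. It does not: under the assumptions above, about 81% of follow-up onsets with a known month go elsewhere. A reader might also infer a systematic bias between arms. The rule is the same in all arms of a double-blind trial, so without a difference between arms in incomplete dating it adds noise or dilutes a contrast.

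**Conclusion.** The point holds in a limited form, and its severity is minor. Read literally, 22.3.5 and 13.1.5 together let events of unknown day be counted as dosing-day events. Under uniform onset during follow-up, roughly 94% (month and year known) to 99% (nothing known) of such placements would be wrong. One misplaced participant moves a row by 1.1 or 2.2 percentage points, depending on the arm. The number of affected events is not given and may be small.

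The conclusion rests on 13.1.5 being silent about imputed dates, not on an instruction to use them. Nor do the documents support calling this the trial's infusion-reaction table, tempting as that is. The visible SAP does not use that name, and SAP 13.1.10 is redacted, so a separate presentation cannot be ruled out. What can be said is that the table's scope matches the definition in Protocol 10.1.3.1. The imputation itself is a sound, cautious choice for TEAE status and need not change.

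**What to change.** In SAP 13.1.5, limit the main count to TEAEs whose recorded, complete start date is the infusion date, still allowing a missing start time. Report TEAEs placed on Day 0 only by imputation in a separate row or footnote per arm, so that no possible reaction is lost. TEAE classification under 13.1.3 and the imputation rules in 22.3.5 stay as they are.

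The cost is a short addition to the SAP text, one filter in the table program and one extra count. No new data are needed. The downside is that a true dosing-day event with an incomplete date appears in the separate count and not in the main one; showing both counts together keeps it visible.

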22.4 Data With Multiple Records

22.4.1 Dose Changes in Medication

Dose changes in medications are recorded on multiple rows in the dataset, with different start and stop dates. When classifying medications into categories (see section 9), each dose is considered a separate medication, and the same medication can be assigned to several categories for the same participant. Within a category, multiple entries contribute as a single count.

22.4.2 Changes in Intensity or Seriousness of Adverse Events

Changes in adverse event intensity or seriousness are recorded on multiple rows in the dataset. An adverse event that changes in intensity or seriousness in a period will contribute to the count of events as a single event.

In summaries of adverse events presented by intensity, the maximum intensity of the adverse event will be used. The maximum intensity is searched for in events with changes, as well as over repeated events based on the preferred term. Adverse events for which information on intensity is missing will be classified as *severe*.

Adverse events for which information on seriousness is missing will be classified as serious.

References

1. Little R and Yau L. Intent-to-treat analysis for longitudinal studies with drop-outs. *Biometrics*. 1996; 52: 1324-1333.
2. Rubin, DB. *Multiple imputation for nonresponse in surveys*. New York: Wiley; 1997.
4. United States Food and Drug Administration (US FDA). *Guidance for Industry: Drug-induced liver injury: premarketing clinical evaluation*. July 2009.

■

[REDACTED]

■

[REDACTED]

■

[REDACTED]

